## 4. BACKGROUND

- **Introduction and rationale**

Older patients visit the emergency department (ED) more frequently in comparison to younger adults [1,2]. Admittance to the ED is associated with risk of negative health outcomes such as functional decline and mortality (the ultimate form of functional decline) [2,3]. This is partly explained by non-specific disease presentation or the presence of frailty, comorbidities or cognitive disorders, which complicates their ED presentation, diagnosis and management [4-6]. It is important to identify older patients with frailty, who are at the highest risk for negative outcomes, in order to be able to take appropriate measures during hospitalization (e.g. fall prevention, physiotherapy, geriatric consultation). Recently it became mandatory to screen all elderly ED patients for frailty as stated by the Health and Youth Care Inspectorate in the Netherlands.

Several geriatric screening tools have been developed to identify frail geriatric patients in the ED [7]. The Acutely Presenting Older Patient (APOP) tool has already been implemented in several Dutch hospitals [8]. This is a validated instrument to predict risk for functional decline and mortality in older patients within three months of presentation in the ED [8, 9]. Like most of the existing screening tools the APOP relies on adequate communication with the patient (or the patients' caregiver). Unfortunately, not infrequently communication with the patient is impaired in the ED due to trauma, confusion, sickness or pre-existent dementia.

An alternative screening tool, based on measurement of sarcopenia with POCUS may provide valuable information in these instances. Sarcopenia is a syndrome characterized by progressive and generalized loss of skeletal muscle mass and strength with a risk of adverse outcomes such as physical disability, poor quality of life and death [10]. Sarcopenia and frailty are two separate conditions, but they overlap especially in the physical aspects of frailty [11]. Therefore, measuring sarcopenia might help in predicting frailty. MRI and CT are regarded as the gold standard to measure muscle mass but they are inconvenient and impossible to perform in everyday clinical practice, especially in the ED [10].

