POCUS has been shown to be a promising technique to measure skeletal muscle mass [12]. It is non-invasive, can be performed at the bedside and has an excellent intra-class correlation coefficient for intra- and inter-observer agreement. [13, 14] Recent studies in a subgroup of hospitalized patients have shown that Qcsa measurements can predict readmission and mortality [15, 16]. ED data however are scarce: Shah et al found in a subset of elderly trauma patients that ultrasound measurements of biceps and quadriceps had modest concordance with the Clinical Frailty Scale (CFS9) [17], whereas Benton et al demonstrated that ultrasound measurements of sarcopenia in older non-trauma patients were (to a variable extend) associated with frailty, falls and subsequent hospitalizations [18].

As POCUS measurement of Qcsa is independent of patient effort and functional or cognitive impairment, it has the potential to be a valuable (alternative) screening tool for functional decline

and mortality in older patients in the ED. However, until now, no data have been published about the relation between Qcsa and functional outcome for patients presenting in the ED.

The aim of this study is to evaluate whether ultrasound measurements of the Qcsa in the ED may be utilized to identify older patients who are at risk for functional decline, ED revisit or death. Our study hypothesis is that Qcsa measurements can predict functional decline, ED revisit or death of older ED patients.

- **Research question**

Primary objective

To evaluate:

- The relation between POCUS measurements of the Qcsa in patients >70 presenting in the ED and ED revisit or death within three months and functional decline within twelve months of their ED visit. Functional decline in this respect is defined as at least one point increase in the Katz ADL-6 survey score or new institutionalization (higher level of assisted living) within twelve months after ED visit.

Secondary objectives

To evaluate:

- To compare the ability of the Qcsa ultrasound to predict functional decline, ED revisit or death in older patients in the ED to the APOP questionnaire (gold standard).
- To compare the added value of Qcsa ultrasound to the APOP questionnaire in the prediction of functional decline, ED revisit or death in older patients in the ED.
- To evaluate the relation between Qcsa ultrasound and physical activity (as scored by KATZ ADL-6 questionnaire).

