## 5.9 Data analysis

 
Justification of sample size (e.g. power analysis)
 

The sample size is calculated based on functional decline and mortality in elderly visiting the ED. We defined functional decline as at least one point increase in the Katz ADL-6 survey score or new institutionalization (higher level of assisted living) within twelve months after ED visit. Prior research in the Netherlands found 9,5% of patients aged <math>\geq 70</math> year died within three months after ED visit and 30,6% experienced functional decline or mortality at 90-day follow-up [8]. With an assumed prevalence of the composed endpoint of 30%, 54 patients are needed to be able to confirm a diagnostic test accuracy with a sensitivity and specificity of <math>>0.8</math> each for a predefined Qcsa cut-off value with a power of 90% and an alfa error of 0.05. To allow for loss of follow-up, 25% more patients will be recruited, resulting in a sample size of 68 patients.

 
Statistical analysis
 

Continuous variables are expressed as mean (95% CI) when normally distributed and median with interquartile range when not normally distributed. Categorical data are presented as absolute

numbers and percentages.

There is a difference in muscle mass between man and woman. The ultrasound measured Qcsa will therefore be adjusted for sex by multiplying female Qcsa with the coefficient 1.484 (male=1) prior to analysis [15]. Diagnostic accuracy of QCSA will be presented as sensitivity and specificity of the optimum Qcsa cut-off point to separate cases (primary endpoint reached after three or twelve months) from non-cases. This optimum cut-off point is calculated as the maximum sum of sensitivity + (1-specificity) using ROC statistics (under the condition of equal costs of misqualification).

A logistic regression model will be used to evaluate whether individual Qcsa predicts functional decline, ED revisit or death. Age, comorbidity, Katz ADL-6, known dementia are defined as clinically relevant covariates and will be included in the regression model.. The predictive ability of the multivariable risk prediction models (e.g. Qcsa prediction model vs APOP prediction model) will be compared.  $\chi^2$  values will be calculated for each prediction model.

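### Section 5.9 names no model containing both APOP and Qcsa, so the one comparison it names cannot show what Qcsa adds to APOP, and the Qcsa-APOP difference has no interval

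*Combined protocol and SAP*

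**What the plan says.** Section 4 (Secondary objectives) lists two objectives that involve APOP. One is the head-to-head: "To compare the ability of the Qcsa ultrasound to predict functional decline, ED revisit or death" against the APOP questionnaire. The other is "To compare the added value of Qcsa ultrasound to the APOP questionnaire in the prediction of functional decline, ED revisit or death". Since the head-to-head already has its own line, the second is most naturally read as incremental value: what Qcsa contributes once APOP is known.

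Section 5.9 (Statistical analysis) plans a logistic regression for Qcsa with four covariates: "Age, comorbidity, Katz ADL-6, known dementia are defined as clinically relevant covariates and will be included in the regression model". APOP is not among them. It then says "The predictive ability of the multivariable risk prediction models (e.g. Qcsa prediction model vs APOP prediction model) will be compared", and that chi-square "values will be calculated for each prediction model". A general two-sided 0.05 threshold follows, tied to no particular test. No section names a model holding both markers, or gives a measure, interval or test for the difference between them.

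**The concern.** A comparison of a Qcsa model with an APOP model shows which predicts better by itself. It does not show whether Qcsa carries information that APOP lacks. Two markers can have any pair of separate chi-squares and be either complementary or almost duplicates.

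Nor does a chi-square per model test the difference. Each tests its own model, and because the Qcsa and APOP models are not nested, subtracting one chi-square from the other is not a likelihood-ratio test. With so few cases, a ranking without an interval is easily over-read.

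At stake are two of the three secondary objectives. One has no named analysis that answers it, and the other has no statement of precision. The model and measure could then be chosen after the data are seen.

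**Working it through.** **Inputs from section 5.9.** 54 evaluable patients, 25% added for loss to follow-up, 30% prevalence. The total reproduces: 54 × 1.25 = 67.5, rounded up to 68. Expected cases: 0.30 × 54 = 16.2 and 0.30 × 68 = 20.4. The point does not rest on how 54 was derived.

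**Assumptions not in the documents.** Both markers normal with equal variance in cases and non-cases; no other covariates; within-group correlation ρ between APOP and Qcsa; APOP/Qcsa AUC of 0.70/0.65 or 0.75/0.70; a 50% event rate as an alternative to 30%.

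**Step 1: overlap changes the combined AUC but not the separate ones.** The standardised separation is d = √2 × Φ⁻¹(AUC). For 0.70, d_A = 0.742; for 0.65, d_Q = 0.545. For the best combination, D² = (d_A² + d_Q² − 2ρ d_A d_Q) / (1 − ρ²) and AUC = Φ(D/√2). Here d_A² + d_Q² = 0.550 + 0.297 = 0.847 and d_A d_Q = 0.404.

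| ρ | D² | Combined AUC | Gain over APOP alone (0.700) |
|---|---|---|---|
| 0 | 0.847 | 0.742 | 0.042 |
| 0.3 | (0.847 − 0.242)/0.91 = 0.664 | 0.718 | 0.018 |
| 0.5 | (0.847 − 0.404)/0.75 = 0.590 | 0.707 | 0.007 |
| d_Q/d_A = 0.735 (redundant) | 0.550 | 0.700 | 0 |

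**Step 2: what the plan would report.** In 2,000 simulated trials per setting (N = 54, 30% events, AUC 0.70/0.65), the mean separate chi-squares across these four correlations were 6.86-7.06 for APOP and 4.19-4.43 for Qcsa. They are flat by construction, since the AUCs are held fixed. That is the point: this output cannot tell the four rows apart.

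**Step 3: what a nested test would report.** Rejection by the 1-df likelihood-ratio test of APOP versus APOP plus Qcsa, over N = 54 or 68, 30% or 50% events and both AUC pairs:

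| ρ | Rejects |
|---|---|
| 0 | about 41-79% |
| 0.3 | about 19-42% |
| 0.5 | about 11-22% |
| Redundant (0.73 or 0.78) | about 5-6% |

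**Step 4: the plan's own target accuracy.** Section 5.9 sizes the study for sensitivity and specificity above 0.8 each. At 0.8/0.8 the binormal model gives d = 2 × Φ⁻¹(0.8) = 1.683 and AUC = Φ(1.683/√2) = 0.883. With Qcsa at 0.88, APOP at 0.70-0.88 and ρ from 0 to 0.5, nested-test power is about 0.69-1.00 (N = 54 at 30% events, N = 68 at 50%).

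**Step 5: precision of the head-to-head.** In the settings of Step 3, the median half-width of the 95% CI for the paired AUC difference was 0.09-0.22, against an assumed true difference of 0.05.

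**The case against.** The best defence is that the gap is silence rather than a wrong method. Section 5.9 speaks of models in the plural and offers Qcsa versus APOP as an example, so a combined model is permitted, and a chi-square per model is an ingredient of a nested test once that model is fitted. The wording of the added-value objective is also awkward. This limits the point: a reader might infer that the plan rules out a combined model, and it does not. But permission is not a plan, and no section names the model, the measure or the interval.

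Three further inferences are tempting and are not supported.

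- *The endpoint window is undefined.* The phrase "primary endpoint reached after three or twelve months" could suggest this. Section 4, section 5.2 and section 5.5.1 all set three months for revisit or death and twelve for functional decline, so the phrase can be read as shorthand. Section 5.1 assesses all outcomes at both times, which leaves some doubt but does not displace those definitions.
- *APOP will be missing in a large share of patients.* Section 4 says that "the APOP relies on adequate communication with the patient" and that "not infrequently communication with the patient is impaired in the ED", but it also names the caregiver as an alternative source. Some APOP results may be missing; the documents give no basis for a number.
- *A nested test would usually be non-significant at this sample size.* That holds only if Qcsa is clearly weaker than planned and correlated with APOP. At the planned accuracy, Step 4 shows reasonable to high power.

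**Conclusion.** The point holds as a gap in specification. The only comparison that section 5.9 names cannot answer the added-value objective in section 4, and the Qcsa-APOP difference has no interval. The logic needs no assumed effect size. The figures illustrate it under a binormal model without covariates: the same separate chi-squares go with a gain in AUC anywhere from 0.042 to zero, and with nested-test rejection anywhere from about 41-79% to 5-6%.

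This is a cheap improvement, confined to secondary objectives. A reader might infer that it weakens the primary analysis; the primary diagnostic-accuracy analysis does not use APOP, and nothing here bears on it.

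**What to change.** Keep the existing text of section 5.9 and add:

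> Added value is assessed in patients with both APOP and Qcsa by comparing a logistic model with APOP to the same model plus sex-adjusted Qcsa, using a likelihood-ratio test (1 df) and the change in AUC with a bootstrap 95% CI. Head-to-head, the AUCs of Qcsa alone and APOP alone are compared in the same patients as the paired difference with 95% CI; a non-significant difference is not read as equivalence. Both analyses use the composite and time windows defined in section 4. APOP enters as its graded result if available, otherwise as high/low. The number of patients without APOP is reported.

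The graded form is preferred because dichotomising discards information that Qcsa can then appear to supply. In simulations where Qcsa was redundant given the full APOP score, the nested test rejected in about 5-7% with the score, but in 13-47% with APOP as high/low (top 20%, 30% or 50% called high).

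The cost is one paragraph and a few lines of R; APOP, Qcsa and the outcomes are already planned data. There are two drawbacks. If Qcsa is weaker than planned, the estimates will be imprecise, so the estimate and interval should lead rather than the p-value. Patients without APOP drop out of both analyses, so the result will not speak for those in whom APOP could not be completed, and their number is unknown in advance.

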A 2-sided P-value <0.05 will be considered statistically significant. Missing data are reported in the results section according to the STROBE 2015 guideline. All statistical analyses will be performed using R or SPSS 26.0 software.

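### Section 5.9 names only a chi-square per model to compare the Qcsa and APOP models; that statistic depends on terms and patients, and the plan does not equate either between the models

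*Combined protocol and SAP*

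**What the plan says.** Section 4 sets two secondary objectives that involve APOP. The first is a head-to-head: "To compare the ability of the Qcsa ultrasound to predict functional decline, ED revisit or death", set against APOP. The second concerns added value: "To compare the added value of Qcsa ultrasound to the APOP questionnaire".

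The analysis for both is in section 5.9: "The predictive ability of the multivariable risk prediction models (e.g. Qcsa prediction model vs APOP prediction model) will be compared". The next sentence says that χ² "values will be calculated for each prediction model". The plan does not say which chi-square is meant (likelihood-ratio, Wald or Hosmer-Lemeshow), how degrees of freedom are handled, or how the values lead to a conclusion.

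Other relevant text in 5.9:
- The terms of the regression model for Qcsa are given: "Age, comorbidity, Katz ADL-6, known dementia are defined as clinically relevant covariates and will be included in the regression model". No list is given for the APOP model.
- ROC methods appear only for choosing the Qcsa cut-off: "using ROC statistics (under the condition of equal costs of misqualification". They are not named for comparing models.
- On incomplete data: "Missing data are reported in the results section". There is no rule on which patients enter which model.

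The documents name no AUC difference, information criterion, optimism correction or nested test.

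**The concern.** A model chi-square (likelihood-ratio or Wald) tests whether a model fits better than one with no predictors, in the data used to fit it. It does not place two models on a common scale of predictive ability. It tends to grow with each term, informative or not, and with each patient. Two non-nested models can be ranked wrongly by it if they differ in either respect.

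Both differences are possible here. The APOP model's terms are unknown. Section 4 notes that "not infrequently communication with the patient is impaired in the ED", so APOP could be missing for patients who have an ultrasound. At stake is the conclusion on whether ultrasound predicts as well as APOP, which the protocol treats as its reference standard. The primary objective is not affected.

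**Working it through.** **Inputs from section 5.9.** Evaluable patients 54; assumed prevalence 30%; recruitment 25% above 54.
- Plan's own figure: 54 × 1.25 = 67.5, rounded up to 68. This reproduces and is not disputed.
- Expected events: 0.30 × 54 = 16.2 and 0.30 × 68 = 20.4.
- Qcsa plus four covariates is at least 5 terms, counting one degree of freedom each. That gives about 16/5 = 3.2 to 20/5 = 4 events per term, so in-sample fit will be optimistic.

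**Assumed, because the documents give no values.** The true AUCs, the fraction with APOP missing, how APOP enters its model, and that the chi-square is the likelihood-ratio one.

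**Step 1: dependence on terms.** For nested models, the likelihood-ratio chi-square cannot fall when a term is added. A useless term adds about 1 on average, so four add about 4 (95th percentile 9.49).

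**Step 2: dependence on patients.** For one predictor of fixed strength, the simulated mean chi-square was about 4.2 at n=40, 5.1 at n=54 and 6.1 at n=68. Subtracting 1 for the single term and dividing by n gives 3.2/40 = 0.080, 4.1/54 = 0.076 and 5.1/68 = 0.075. The part above 1 is therefore roughly proportional to n.

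**Step 3: can the ranking be wrong?** Take two equally informative predictors and give one model four extra noise terms (600 runs per setting, about 30% events). AUC was measured in 20,000 new patients.

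| n | Larger model has larger chi-square | Mean chi-square, larger vs smaller | AUC in new patients, larger vs smaller |
|---|---|---|---|
| 54 | 75% | 9.5 vs 4.9 | 0.62 vs 0.66 |
| 68 | 74% | 10.6 vs 6.2 | 0.62 vs 0.66 |

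The larger model usually has the larger chi-square and predicts worse on average. With no extra terms the shares were 48% and 52%.

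**Step 4: sensitivity to the APOP model's terms.** Here 16 cases and 38 non-cases are used. The Qcsa model is five noise terms (mean chi-square about 5.5). The entry is the share of trials in which it has the larger chi-square. Ranges show repeat simulations of 3,000 to 4,000 trials.

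| APOP true AUC | APOP as one term only | Same four covariates in both models |
|---|---|---|
| 0.50 | 93% | 52% |
| 0.65 | 63% | 21% |
| 0.70 | 41–43% | 8–10% |
| 0.75 | 21–23% | 2–4% |

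**Step 5: sensitivity to the patients used.** Two one-term models have the same true AUC (0.75, correlation 0.3), n=54, with APOP missing at random. The entry is the share of trials in which Qcsa has the larger chi-square.

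| APOP missing | Each model on its own patients | Both models on the same patients |
|---|---|---|
| 10% | 54–56% | about 50% |
| 20% | 61–62% | about 50% |
| 30% | 65–67% | about 50% |

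At 20% missing, APOP's mean chi-square falls from about 10.3 to 8.6. Step 2 predicts 1 + 0.8 × (10.3 − 1) = 8.4, which is close.

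**The case against.** The strongest reply is that the plan commits to none of the conditions that produce the large figures.

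- **Terms.** Section 5.9 calls both models multivariable, which sits badly with a one-term APOP model. With the same covariates on both sides, most of the effect in step 4 disappears. This stands.
- **Decision rule.** Nothing says that the larger chi-square wins. Section 5.9 sets a two-sided 0.05 threshold, so each chi-square might be read with its degrees of freedom and P-value. Ranked by P, even against a one-term APOP score, the noise model wins 55%, 21%, 9% and 3% of trials at AUC 0.50, 0.65, 0.70 and 0.75, and it reaches P<0.05 in about 8%. This also stands, but a P-value against no predictors still does not estimate the difference in predictive ability. A Hosmer-Lemeshow chi-square would test calibration and would not rank the models either.
- **Patients.** Section 4 allows a caregiver to supply the information for APOP. Section 5.1 collects APOP and Katz together with the ultrasound. The Qcsa model itself needs Katz ADL-6, so a patient who cannot answer may drop out of both models. Separate complete-case sets are an inference from the plan's silence.

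A reader might infer that the planned comparison is tilted towards Qcsa on both counts. The documents do not support that. It would need an APOP model with fewer terms and APOP missing more often than the Qcsa model's inputs, and neither is stated. Entered item by item, APOP could be the larger model.

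**Conclusion.** The concern holds as a fault of the measure and of the specification. The only statistic named for the head-to-head is an in-sample fit statistic that depends on the number of terms and patients, and the plan equates neither between the two models. The ranking can therefore be wrong.

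No bias of a given size or direction has been shown. The illustrations run from material (about 42% and 61%) to small or nil (about 10% and 50%), depending on choices that the plan leaves open. They rest on a likelihood-ratio chi-square, a reading in which the larger value is preferred, and the assumed AUCs and missing fractions. If both models had the same number of terms and the same patients, the distortion would largely go, but there would still be no estimate of the difference and no interval. The point should be settled before analysis; it concerns secondary objectives only.

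**What to change.** Replace the chi-square sentence in section 5.9 with:

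> The Qcsa and APOP models will carry the same covariates and be fitted in the same patients (Qcsa, APOP, covariates and outcome all available). Predictive ability will be compared by the difference in bootstrap optimism-corrected AUC with a paired bootstrap 95% CI. Added value of Qcsa will be tested by a likelihood-ratio test of APOP versus APOP plus Qcsa in those patients. Model chi-squares will not be used to rank non-nested models.

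State also how APOP enters its model (one score or separate items). With Qcsa as a single term, the added-value test has 1 degree of freedom and a critical value of 3.84. A chi-square is appropriate there because the models are nested.

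Cost: wording and a few lines of code, with no new data or patients. The comparison is limited to patients with both tests, so the number left out should be reported. The corrected figures will look less favourable than the in-sample ones, and with about 16 to 20 events the interval is likely to be wide.

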### 3. ABSTRACT (max. 250 words)

- **Background**

Older people visit the ED more frequently than younger people and have a higher risk of functional decline, ED revisit or death. Several screening tools (such as VMS and APOP) have been developed to identify patients at the highest risk of adverse outcomes. Almost all require adequate communication with the patient, which is not always possible, for example when elderly patients present with a delirium. Point of Care Ultrasonography (POCUS) may be a valuable alternative screening tool in these instances.

- **Main research question**

To identify whether POCUS measurement of the rectus femoris muscle cross-sectional area (Qcsa) can be used as an alternative screening tool to predict functional decline, ED revisit or death in elderly patients in the ED.

- **Design (including population, confounders/outcomes)**

This is a single centre prospective trial. Patients >70 years and older presenting in the ED of the UMCG hospital who are participating in the Acutelines bio-databank are eligible for inclusion. 68 patients will be included. Data will be extracted from the Acutelines bio-databank. A trained physician will perform ultrasound measurements in a standardized way.

- **Expected results**

The aim of this study is to evaluate whether ultrasound measurements of the Qcsa can be utilized to identify older patients who are at risk for functional decline, ED revisit or death.

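### The trial is sized to confirm sensitivity and specificity above 0.8, but no planned analysis tests or interprets them against any value; the only inferential criterion is p<0.05, which in the regression tests association

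*Combined protocol and SAP*

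**What the plan says.** The main research question in section 3 is whether Qcsa "can be used as an alternative screening tool to predict functional decline, ED revisit or death". The sample-size paragraph of section 5.9 matches it: "54 patients are needed to be able to confirm a diagnostic test accuracy with a sensitivity and specificity of" more than 0.8, "each for a predefined Qcsa cut-off value with a power of 90% and an alfa error of 0.05". The 54 is raised by 25% to 68 for loss to follow-up.

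The statistical analysis paragraphs of 5.9 contain three relevant statements:

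- On accuracy: "Diagnostic accuracy of QCSA will be presented as sensitivity and specificity of the optimum Qcsa cut-off point". The cut-off is the optimum found by ROC analysis in the study data. No confidence interval, null value, test or comparison with 0.8 follows.
- On prediction: "A logistic regression model will be used to evaluate whether individual Qcsa predicts functional decline, ED revisit or death". Age, comorbidity, Katz ADL-6 and known dementia enter the model.
- On inference: "A 2-sided P-value <0.05 will be considered statistically significant".

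The hypothesis in section 4 is that Qcsa measurements are predictive, with no minimum accuracy. The primary objective there is the relation between Qcsa and the outcomes.

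**The concern.** The design target and the analysis do not meet. The study is sized to confirm an accuracy, yet no analysis can confirm or fail to confirm it. The one analysis with a significance criterion answers a different question, whether Qcsa is related to outcome at all.

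A marker can be clearly associated with outcome and still be a poor screen. At sensitivity and specificity of 0.70 it misses 30% of cases and falsely flags 30% of non-cases. With no stated rule, the step from results to a statement about screening use is left until after the data are seen. The only formal criterion available is then one that a marker below the target will often meet.

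**Working it through.** **The plan's own figures.** 54 × 1.25 = 67.5, so 68 reproduces. The 54 does not follow from the stated inputs, because no null value is given and the sample-size sentence does not state sidedness. One route that reaches it assumes a null of 0.5 against 0.8, one-sided, with a Wald formula: (1.645 + 1.282)² × 0.8 × 0.2 / 0.3² = 15.2, so 16 cases, and 16 / 0.30 = 53.3, so 54. The two-sided version gives 18.7, so 19 cases and 64 patients. The null of 0.5 is an assumption here; only the sponsor can say what was used.

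**Inputs for the check.** From 5.9: 54 evaluable patients (or all 68), 30% cases, two-sided 0.05. This gives about 16 cases and 38 non-cases, or 20 and 48. Assumed: Qcsa is normal with equal variance in cases and non-cases, and the cut-off lies midway, so the group separation is 2 × z(sensitivity).

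**Smallest difference that is significant.** t(0.975, 52) × √(1/16 + 1/38) = 2.007 × 0.298 = 0.598 SD. This corresponds to AUC Φ(0.598/√2) = 0.66 and sensitivity = specificity = Φ(0.299) = 0.62.

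**Chance of p<0.05, Qcsa as the only predictor.** At true 0.70 the separation is 2 × 0.524 = 1.049 SD.

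- n = 54: 1.049 / 0.298 = 3.52, and Φ(3.52 − 2.01) ≈ 0.93.
- n = 68: 1.049 / √(1/20 + 1/48) = 3.94, and Φ(3.94 − 2.00) ≈ 0.97.

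Simulated logistic regression (Wald test):

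| True sensitivity = specificity | n = 54 | n = 68 |
|---|---|---|
| 0.65 | 68–69% | 80% |
| 0.70 | 90–91% | 96–97% |
| 0.75 | 99% | >99% |

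**Chance of p<0.05 with four covariates, true 0.70.** The documents give no figures for how strongly the covariates predict outcome or correlate with Qcsa, so these are simulations under assumptions:

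- Unrelated to outcome: about 90% at n = 54, rising to about 98% if they are correlated with Qcsa.
- Each shifted by 0.5 SD between cases and non-cases, correlation 0.3 with Qcsa: about 35% at n = 54 and 44% at n = 68 if the covariates are mutually uncorrelated. If they are also correlated with each other at 0.3, about 66% and 78%.

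The range is therefore roughly one third to over 90%. It is not a bound; stronger covariates push it lower.

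**Comparison with an accuracy criterion.** At a fixed cut-off with 16 cases and 38 non-cases and true values of 0.70, both observed values exceed 0.8 with probability P(≥13 of 16) × P(≥31 of 38) = 0.246 × 0.079 = 0.02. At the best cut-off chosen in the same data the figure is about 6%. About 95% of significant single-predictor results at true 0.70 would thus show an observed sensitivity or specificity of 0.8 or less.

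**The case against.** The strongest defence is that the plan contains no rule of the kind a reader might infer. The p<0.05 sentence is a general convention for all tests, and nowhere do the documents say that a significant Qcsa coefficient means Qcsa is usable as a screen. That stands. The tempting stronger reading, that the plan will declare a sub-target marker fit for screening about nine times in ten, is not supported. The declaration is inferred, and the nine in ten belongs to a single-predictor model, whereas 5.9 says that four covariates will be included.

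Second, sensitivity and specificity will be reported, so a reader would usually see values below 0.8. This also stands and limits the harm. It does not close the gap: the values come without intervals, at a cut-off chosen to favour them, and no text says what follows when p<0.05 and the accuracy falls short.

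Third, testing association fits the primary objective in section 4, which speaks of a relation. That is fair for the objective, but it does not answer the screening question in section 3 or use the accuracy that the sample size was built on.

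**Conclusion.** The concern holds as a mismatch between design target and analysis. Sensitivity and specificity above 0.8 drive the sample size but are neither tested nor interpreted against any value, and the only inferential criterion addresses association. At a true 0.70/0.70 that criterion is met about 90% of the time with 54 evaluable patients and 97% with 68 in a single-predictor model, and from roughly a third to over 90% with the planned covariates. These figures rest on 30% prevalence, normally distributed Qcsa and assumed covariate effects. The mismatch can be read directly from 5.9 and does not depend on them. The documents do not commit to reporting significance as fitness for screening; the defect is that nothing rules it out. It should be corrected before the analysis.

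**What to change.** Amend 5.9 as follows:

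1. Report sensitivity and specificity with exact 95% confidence limits at the predefined cut-off, with its value stated. If the cut-off is chosen in the study data, correct the estimates and limits by a named method, for example a bootstrap that repeats the choice in each resample.
2. State the null value and sidedness used to obtain 54.
3. Answer the screening question by whether the lower limits of both measures exceed that null, and show the estimates beside the 0.8 target.
4. Report a significant regression coefficient without this as an association only.

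I would not also require both point estimates to be at least 0.8. With 16 cases and 38 non-cases and true values of 0.80, that succeeds with probability 0.598 × 0.500 = 0.30.

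The change is wording, with no new patients or data. The cost is that a positive screening conclusion becomes less likely. As an illustration, take an assumed null of 0.5, a fixed cut-off and two-sided exact 95% limits, so that at least 13 of 16 and 26 of 38 are needed. The rule is then met with probability 0.598 × 0.971 = 0.58 at true 0.80, and 0.246 × 0.659 = 0.16 at true 0.70. If 54 was derived one-sided, the matching limits need 12 of 16 and 25 of 38, which gives 0.798 × 0.988 = 0.79 at true 0.80. This is why sidedness must be stated. If 0.8 is itself the null, the planned size cannot serve: with a true value of 0.90, two-sided 0.05 and 90% power, about 137 cases are needed, or 137 / 0.30 ≈ 457 patients.
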